LOD	limit of detection
LOQ	limit of quantitation
MAD	multiple ascending dose
MedDRA	medical dictionary for regulatory activities
NOEL	No observed effect level
PBO	Placebo
PD	protocol deviation(s)
PK	pharmacokinetics
PKAP	PK analysis plan
PT	preferred term
Q1, Q3	first quartile, third quartile
QD	once daily
SAD	single ascending dose
SAE	serious adverse event
SAP	statistical analysis plan
SD	standard deviation
SE	standard error
SOC	system organ class
TE	treatment-emergent
TEAE	treatment-emergent adverse event

TFLs tables, figures, and listings
WHO world health organization

1 INTRODUCTION

This statistical analysis plan (SAP) describes the statistical analysis methods and data presentations to be used in tables, figures, and listings (TFLs) in the clinical study report (CSR) for Study ABI-4334-101. This SAP is based on the original study protocol version 1.0, dated 16 June 2022 and the electronic case report form (eCRF) version 1.0, dated 18 October 2022. The SAP will be finalized before database lock. Any changes made after the finalization of the SAP will be documented in the CSR.

1.1.1 Study Objectives

The primary objective is:

- To assess the safety and tolerability of orally administered ABI-4334 in healthy subjects following single (Part A, single ascending dose [SAD]) and 8-day multiple (Part B, multiple ascending dose [MAD]) oral doses.

The secondary objectives are:

- To characterize the pharmacokinetics (PK) of ABI-4334 in plasma following single doses and 8-day multiple doses in healthy subjects.
- To evaluate the effect of food on the PK of ABI-4334 following a single dose in healthy subjects (Part A food-effect cohort(s) only).

[figure not shown]
The exploratory objectives are:

- To evaluate the PK of ABI-4334 in urine following 8-day multiple doses in healthy subjects (Part B, MAD).

1.2 Study Design

This is a Phase 1, first-in-human (FIH), randomized, blinded, placebo (PBO)-controlled, single- and multiple-dose, dose escalation study of ABI-4334 in healthy subjects. Part A is designed to assess the safety, tolerability, and PK profile of ABI-4334 following SAD in healthy subjects, as well as the effect of food on ABI-4334. Part B is designed to assess the safety, tolerability, and PK profile of ABI-4334 following MAD in healthy subjects. Figure 1 **Figure 1** provides an overview of the 2-Part study design.

Figure 1. Overview of Study Design – Parts A & B (SAD and MAD)

Abbreviations: BID=twice daily; MAD=multiple ascending dose; PBO=placebo; QD=once daily; SAD=single ascending dose; TBD=to be determined

*Applies to all SAD cohorts, except Cohort A7, which will only have 6 active subjects (ie, randomized to ABI-4334), no PBO subjects.

[figure not shown]
**Part B dosing may commence prior to Part A being completed.

1.2.1 Part A (SAD in Healthy Subjects)

Part A of the study will enroll up to 5 fasted cohorts, ie, Cohorts A1-A5, and up to 2 fed cohorts to evaluate food effect, ie, Cohort A6 (with subjects from a previous fasted cohort), and an additional cohort, ie, Cohort A7, if needed (with new subjects).

The first cohort of Part A, ie, Cohort A1, will evaluate a single dose of 30 mg ABI-4334. Dose levels for subsequent cohorts will be determined based on interim cohort review performed by an unblinded Data Review Committee (DRC) between SAD cohorts for purposes of dose escalation. In no case would a dose escalation be greater than 3.3-fold compared with the previous dose. The maximum dose of ABI-4334 to be evaluated in Part A (SAD) will not exceed the exposures observed in dogs at the no observed effect level (NOEL) dose of 30 mg/kg/day, or 1000 mg/day, whichever is lower. Figure 2 provides an overview of Part A study design.

Figure 2. Study Design Schematic – Part A (SAD in Healthy Subjects)

Abbreviations: DRC=Data Review Committee; PBO=placebo; SAD=single ascending dose

Each of the Cohorts A1-A5 will enroll 8 healthy subjects who will be randomized in a 6:2 ratio to receive a single oral dose of the study drug, ie, ABI-4334 (6 subjects) or PBO (2 subjects) in a fasted state, followed by a 7-day follow-up period. Subjects will remain confined to the study clinic from Days -1 to 4, with outpatient follow-up visits. Dosing of a subsequent SAD cohort can begin at least 8 days after dosing of the sentinel subjects from the previous cohort (see below).

Because this is a FIH study, a sentinel dosing approach will be utilized for each Cohort A1-A5, where initially only 2 subjects per cohort will be dosed (one receiving ABI-4334 and one receiving PBO). These sentinel subjects will be observed for a minimum of 3 days postdose to ensure acceptable tolerability of the study drug, as determined by the DRC, before dosing of the remaining subjects within the cohort can proceed.

The DRC will select a single dose level from Cohorts A1-A5 for evaluation of food effect. The selection of this dose level can be made prior to completion of all fasted SAD cohorts and will be based on a preliminary evaluation by the DRC of the available safety, tolerability, and PK data from selected Cohorts A1-A5. Subjects who complete participation in this selected cohort will be asked to return to the study site to be enrolled into the food-effect cohort (ie, Cohort A6), following a minimum of 7-day washout period since their last study drug dose. While Baseline evaluations will be conducted prior to dosing in Cohort A6, repeat assessment of all study eligibility criteria will not be performed. Returning subjects will retain their original subject number and randomized treatment assignment. After the Day 7 visit in the original cohort (from Cohort A1-A5), the study drug will be administered 30 minutes after the complete consumption of a high fat meal (approximately 50% calories from fat).

If there is an insufficient number of subjects from previous fasted SAD cohorts (ie, A1-A5), who are willing to participate in Cohort A6, then a separate Cohort A7 may be enrolled, comprising 6 new subjects meeting the study eligibility criteria, who will all receive ABI-4334. Cohort A7 will

involve a two-period crossover assessment of food effect (ie, Period 1: dosing under fasted or high fat-fed conditions; Period 2: dosing under condition opposite of Period 1), with a minimum 7-day washout period between dosing in Period 1 and Period 2, and a 7-day postdose follow-up in Period 2.

[figure not shown]
1.2.2 Part B (MAD in Healthy Subjects)

Part B dosing may commence prior to Part A being completed. The dose level and dosing schedule for the first cohort of Part B, ie, Cohort B1, will be determined based on emergent safety, tolerability, and PK data from completed Part A cohorts, with the daily dose at least 2-fold lower than a Part A dose level deemed safe and tolerable.

Both cohorts planned for Part B, ie, Cohort B1 and Cohort B2, will enroll 8 healthy subjects who will be randomized in a 6:2 ratio to receive oral daily doses of the study drug, ie, ABI-4334 (6 subjects) or PBO (2 subjects), for 8 consecutive days, followed by a 7-day follow-up period. Dosing may occur under fasted or fed conditions, depending on the results from the food-effect cohort(s) in Part A. Subjects will remain confined to the study site from Days -1 to Day 11 (ie, 3 days post last day of dosing), with outpatient follow-up visits.

The dose level and dosing schedule for Cohort B2 will be based on an evaluation by the DRC of safety data from Day 1 through Day 8 for Cohort B1 and all available safety data for preceding cohorts. In addition, PK data through 24 hours after dosing on Day 8 for Cohort B1 and available PK data for preceding cohorts will be reviewed. In no case would the dose escalation be greater than 3.3-fold compared with the previous dose. Dosing of Cohort B2 can begin at least 11 days after the first day dosing of subjects in Cohort B1. The maximum dose of ABI-4334 to be evaluated in Part B (MAD) will not exceed the exposures observed in dogs at the NOEL dose of 30 mg/kg/day, or 1000 mg/day, whichever is lower. Figure 3 provides an overview of Part B study design.

Figure 3. Study Design Schematic – Part B (MAD in Healthy Subjects)

Abbreviations: DRC=Data Review Committee; PBO=placebo

1.3 Sample Size and Power

Approximately 8 healthy subjects will be enrolled in each cohort. Approximately 6 subjects will be enrolled in Cohort 7 of Part A if necessary. For this FIH study, the sample sizes are similar to those previously utilized for this type of study and are not based on statistical considerations.

1.4 Methods of Assigning Subjects to Treatment

1.4.1 Randomization

For cohorts A1-A4 and B1-B2, all subjects will be assigned a unique subject number at Screening and will be randomized to treatment with either ABI-4334 or placebo, upon meeting all protocol eligibility requirements. Randomization will be performed by an unblinded pharmacist. Subjects returning as part of cohort A6 will retain their original subject number and randomized treatment assignment.

Subjects in cohort A7 will take only ABI-4334. Subjects will be randomized, with 3 subjects being fed then fasted, and 3 subjects fasted then fed, in each of the two periods.

1.4.2 Blinding

Except for DRC members, unblinded site pharmacists, and other personnel administering treatment randomization, all study team members will be blinded to individual subject treatment assignments for cohorts A1-A4 and cohorts B1-B2 throughout the duration of the study. The

study subjects will also be blinded to their treatment assignment throughout the duration of the study.

The DRC will be unblinded to individual subjects' treatment assignments throughout the study to ensure timely analysis of any emergent safety and tolerability issues, and completion of the prespecified safety and PK data reviews. The unblinded individuals will be identified in the DRC charter along with their specific roles and responsibilities. The clinical research organization's (CRO) Medical Monitor may be unblinded to individual subjects' treatment assignments where required for assessment of emergent safety/tolerability issues.

2 TYPE OF PLANNED ANALYSIS

2.1 DRC Interim Analyses

The DRC will review the cumulative safety and PK data from each previous cohort to determine dose level and dosing schedule for the subsequent cohort(s). Details concerning the DRC will be documented in the DRC charter.

2.2 Final Analysis

The final analysis will be performed after all subjects have completed the study, outstanding data queries have been resolved or adjudicated as unresolvable, and the data have been cleaned and finalized.

3 GENERAL CONSIDERATIONS FOR DATA ANALYSES

Analysis results will be presented using descriptive statistics. For categorical variables, the number and percentage of subjects in each category will be presented; for continuous variables, the number of subjects (n), mean, standard deviation (SD) or standard error (SE), median, first quartile (Q1), third quartile (Q3), minimum, and maximum will be presented.

Summary tables will be presented by cohort and treatment. For cohort A7, summary tables will be presented fasting order (i.e. “fed,fasted” or “fasted,fed”).

No formal inference is planned in this study. Hence, no multiplicity adjustment is required.

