5.1.6 Summaries of Adverse Events and Deaths

Treatment-emergent AEs will be summarized based on the Safety Analysis Set.

A brief, high-level summary of the number and percentage of subjects who experienced at least 1 TEAE in the categories described below will be provided by treatment and cohort. All deaths observed in the study will also be included in this summary. The number and percentage of subjects will be provided by SOC, PT, treatment, and cohort for each AE category and also by PT only in descending order of total frequency:

- TEAEs
- TEAEs by severity grade
- TEAEs related to study drug
- TE SAEs
- TE SAEs related to study drug
- TEAEs leading to study drug discontinuation
- TEAEs leading to study discontinuation
- TEAEs leading to death (ie, outcome of death)
- COVID-19 specific TEAEs
- COVID-19 specific TE SAEs

Multiple events will be counted only once per subject in each summary. Adverse events will be summarized and listed first in alphabetic order of SOC, and then by PT in descending order of total frequency within each SOC. For summary by severity grade, the most severe non-missing grade will be used for those AEs that occurred more than once in an individual subject during the study.

Data listings will be provided for the following:

- All AEs
- All treatment-related AEs
- All SAEs
- All treatment-related SAEs
- All AEs with severity of Grade 3 or higher
- All AEs leading to discontinuation of study drug
- All AEs leading to discontinuation of study
- All AEs leading to death (ie, outcome of death)
- All Deaths

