5.2.1.2 Summaries of Laboratory Abnormalities

Treatment-emergent graded laboratory abnormalities will be summarized (number and percentage of subjects) by cohort, lab test, and treatment group; subjects will be categorized according to the most severe post-baseline abnormality grade for a given lab test.

For all summaries of laboratory abnormalities, the denominator is the number of subjects with nonmissing post-Baseline values.

The maximum post-Baseline grade observed will be tabulated for each laboratory test, and percentages will be based on the number of subjects with a post-Baseline evaluation of the specific laboratory test. A by-subject listing of graded laboratory abnormalities will be provided by cohort, subject number, and visit in chronological order. This listing will include all test results that were collected throughout the study for the lab test of interest, with all applicable severity grades displayed.

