5.2.3 Summaries of Numeric Laboratory Results

Descriptive statistics will be provided by treatment and cohort for each laboratory test specified in the study protocol as follows:

- Baseline values
- Values at each post-Baseline visit
- Change from Baseline at each post-Baseline visit

A Baseline laboratory value will be defined as the last measurement obtained on or prior to the date/time of first dose of study drug. Change from Baseline to a post-Baseline visit will be calculated for any post-Baseline visit including follow-up visits. For Cohort A7 Period 2, Period 2 Baseline and Change from Period 2 Baseline will be used instead.

In the case of multiple values in a visit day, data will be selected for analysis as described in [Section 3.5.6](#).

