5.3 Body Weight and Vital Signs

Descriptive statistics will be provided by treatment and cohort for body weight, BMI, and vital signs (systolic and diastolic blood pressure [mmHg], pulse [beats/min], respiration [breaths/min], and body temperature [°C]) as follows:

- Baseline value
- Values at each post-Baseline visit
- Change from baseline at each post-Baseline visit

A Baseline value will be defined as the last available value collected on or prior to the date/time of first dose of study drug. Change from Baseline to a post-Baseline visit will be calculated for any post-Baseline visit including follow-up visits.

For Cohort A7 Period 2, Period 2 Baseline and Change from Period 2 Baseline will be used instead.

In the case of multiple values in an analysis window, data will be selected for analysis as described in [Section 3.5.6](#).

A by-subject listing of vital signs will be provided by cohort, subject number, and visit in chronological order. In the same manner, a by-subject listing of body weight, height, and BMI will be provided separately.

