5.5 Electrocardiogram Results

A shift table of the Investigators' assessment of electrocardiogram (ECG) results at each visit compared with Baseline values will be presented by treatment and cohort using the following categories:

- normal
- abnormal (not clinically significant)
- abnormal (clinically significant)
- missing/not done

The number and percentage of subjects in each cross-classification group of the shift table will be presented. Subjects with a missing value at Baseline or post-Baseline will not be included in the denominator for percentage calculation.

A by-subject listing for ECG assessment results will be provided by cohort, subject number, and visit in chronological order.

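### A pooled placebo column would be a cheap gain in precision for safety tables that set 6 active subjects beside a planned 2 on placebo

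*Combined protocol and SAP*

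**What the plan says.** The general rule in SAP section 3 is "Summary tables will be presented by cohort and treatment". The later sections repeat it:

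- Adverse events (SAP 5.1.6): subject counts "in the categories described below will be provided by treatment and cohort".
- Graded laboratory abnormalities (SAP 5.2.1.2): "Treatment-emergent graded laboratory abnormalities will be summarized (number and percentage of subjects) by cohort, lab test, and treatment group". Direct bilirubin (SAP 5.2.2) and numeric laboratory results (SAP 5.2.3) use the same split.
- Vital signs and weight (SAP 5.3): "Descriptive statistics will be provided by treatment and cohort for body weight, BMI, and vital signs".
- ECG (SAP 5.5): investigator assessments "at each visit compared with Baseline values will be presented by treatment and cohort".

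The allocation is the same in both parts. SAP 1.2.1 gives each of Cohorts A1-A5 6 active and 2 placebo subjects. SAP 1.2.2 says that subjects in B1 and B2 "will be randomized in a 6:2 ratio to receive oral daily doses of the study drug", again 6 and 2. Cohort A7 has no placebo arm (SAP 1.2). Cohort A6 brings back subjects from an earlier cohort on their original assignment.

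No section of the available text names a pooled or combined placebo group. The SAP contents page lists a section 9 of appendices, but neither that section nor the table shells were available.

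**The concern.** Safety and tolerability is the primary objective, and the primary endpoint (Protocol 3.2.1) is a set of proportions. Under the stated layout, each active dose is read against two placebo subjects. With exactly two, a placebo percentage can take only three values, so one chance event moves it by 50 points. Placebo subjects from the other fasted cohorts took placebo under the same part and the same fasting condition. Showing them together would give a steadier background for each dose.

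What is at stake is how easily a reader of the study report can tell a dose-related finding from background. No hypothesis test, error rate or power statement depends on it, because the SAP plans none.

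**Working it through.** **Inputs.**
- Allocation 6:2 in A1-A5 and in B1-B2: SAP 1.2.1 and 1.2.2.
- Number of fasted cohorts: five in SAP 1.2.1, but SAP 1.4.1 and 1.4.2 list A1-A4 as the randomised and blinded fasted cohorts. Protocol 4.2 allows cohorts not to be enrolled, and Protocol 7.1.2 allows some withdrawn subjects to be replaced.
- Background event rate p: not given in the documents. Assumed 30%, with 20% to 40% as the range, and 5% and 10% as a check.

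**Head count.** Part A: 5 × 8 + 6 = 46, since A6 re-uses subjects. Part B: 2 × 8 = 16. Both agree with Protocol 5.1. The placebo pool is therefore 5 × 2 = 10 or 4 × 2 = 8 in Part A, and at most 2 × 2 = 4 in Part B.

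**Precision.** With n placebo subjects and a common rate p, SE = √[p(1−p)(1/6 + 1/n)]. At p = 0.3, n = 2 gives √(0.21 × 0.6667) = 0.374, n = 8 gives √(0.21 × 0.2917) = 0.247, and n = 10 gives √(0.21 × 0.2667) = 0.237. The reduction against n = 2 is 1 − √[(1/6 + 1/n)/(1/6 + 1/2)], whatever p is. Its limit is 1 − √[(1/6)/(2/3)] = 50%, because the active group stays at 6.

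**Chance gaps.** Let x ~ Bin(6, p) and y ~ Bin(n, p) be independent, with no drug effect. The quantity is P(|x/6 − y/n| ≥ 0.5), summed exactly. For n = 2 and p = 0.3:
- Active worse: P(y=0)P(x≥3) + P(y=1)P(x=6) = 0.49 × 0.2557 + 0.42 × 0.0007 = 0.126.
- Placebo worse: P(y=1)P(x=0) + P(y=2)P(x≤3) = 0.42 × 0.1176 + 0.09 × 0.9295 = 0.133.
- Total 0.259.

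**Zero placebo events.** The exact 95% upper limit for 0/n is 1 − 0.025^(1/n).

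| Placebo n | SE of difference, points, at 30% (20%, 40%) | SE reduction | P(gap ≥ 50 points), either direction, at 30% (20%, 40%) | Upper limit, 0/n |
|---|---|---|---|---|
| 2 | 37.4 (32.7, 40.0) | – | 25.9% (18.7%, 32.0%) | 84% |
| 4 | 29.6 (25.8, 31.6) | 21% | 13.7% (10.0%, 14.8%) | 60% |
| 8 | 24.7 (21.6, 26.5) | 34% | 5.9% (3.8%, 6.5%) | 37% |
| 10 | 23.7 (20.7, 25.3) | 37% | 4.2% (2.5%, 5.3%) | 31% |

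**Rarer events, 6 versus 2.**
- p = 10%: active worse 0.81 × 0.01585 = 0.0128; placebo worse 0.18 × 0.5314 + 0.01 × 0.9987 = 0.1056; total 0.1185, about 12%.
- p = 5%: active worse 0.9025 × 0.00223 = 0.0020; placebo worse 0.095 × 0.7351 + 0.0025 × 0.9999 = 0.0723; total 0.0743, or 7.4%.

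The SE reductions also apply to a difference in mean change from baseline if the standard deviations are equal.

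**The case against.** The strongest reply is that this is a preference about layout. Tables by cohort are legitimate when cohorts differ in dose, calendar time and perhaps tablet count. Placebo counts can be added by hand and by-subject listings are planned. That stands, and it is why the point ranks low. It is not a complete answer, because pooled medians and quartiles cannot be rebuilt from the cohort columns.

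A second reply is that the appendix or shells may already define a pooled column. This cannot be excluded, so the fix is conditional on it.

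Three stronger readings are tempting, and the documents do not support them:

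- *That the SAP contradicts the protocol.* Protocol 10.4 and 10.4.4 ask for summaries per treatment, and Protocol 3.2.1 for results per part. These fit a pooled column but do not require one, so there is no conflict.
- *That false signals of drug harm will be frequent.* The 25.9% covers both directions, and only 12.6 points of it are active looking worse. At rates of 5% and 10% the two-directional figure falls to 7.4% and about 12%, and nearly all of that is placebo looking worse.
- *That dose escalation is compromised.* An unblinded data review committee reviews cumulative safety and PK data under its own charter (SAP 1.4.2 and 2.1). Its decisions do not rest on the final report tables.

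**Conclusion.** The point holds as an optional, low-severity improvement in descriptive precision. In Part A, pooling cuts the standard error of each active-minus-placebo contrast by 34% with four fasted cohorts or 37% with five. At an assumed rate of 30%, it lowers the chance of a spurious gap of 50 points or more, in either direction, from 25.9% to 5.9% or 4.2%.

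The gain in Part B is smaller: at most 4 placebo subjects, a 21% reduction and a chance of 13.7%. There is no gain there if B1 and B2 differ in dosing schedule or in fed or fasted state, since they should then not be pooled.

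The probabilities rest on the assumed event rates and on a common rate in the two groups. The percentage reductions in standard error depend only on the group sizes, given a common rate or equal standard deviations. Everything is illustrative, because the study plans no formal inference. The conclusion lapses if the SAP appendix or the shells already provide the column.

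**What to change.** Unless the appendix or shells already provide it, add to SAP section 3 that the adverse event, laboratory, vital-sign and ECG summaries also show a pooled placebo column. It would cover the placebo subjects actually dosed in the fasted Cohorts A1-A5 and stand beside the existing cohort-level columns, which stay. The same text should state that:

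- fed-period placebo data from A6 are left out, so that no returning subject is counted twice;
- Part A and Part B placebo are not combined;
- B1 and B2 placebo are pooled only if the dosing schedule and the fed or fasted state match, and are otherwise shown separately;
- a footnote lists the contributing cohorts.

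The cost is one column and one footnote per table. The downside is an assumption that placebo subjects are comparable across cohorts dosed at different times and possibly with different numbers of tablets. The retained cohort columns let a reader check this.
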